Modafinil (Provigil, 1997) is a novel drug which has a demonstrable efficacy in the treatment of daytime sleepiness associated with narcolepsy (Benerjee et al., 2004). Studies with healthy volunteers,

including those conducted by our research group, showed that modafinil improves some aspects of neuropsychological task performance, possibly through improved inhibitory control (Turner et al., 2003; Baranski et al., 2004; Muller et al., 2004; Randall et al., 2005). For instance, Turner et al. (2003) assessed the cognitive enhancement potential of modafinil on sixty young healthy male volunteers who either received a single oral dose of placebo, or 100mg, or 200mg of modafinil before undertaking tasks on working memory and attention. Modafinil significantly improved performance of digit span, visual pattern recognition memory, spatial planning and stop signal reaction time. It also significantly improved performance on tests on decision making and delayed matching to sample.

Modafinil also had a significant beneficial effect on working memory and executive attention in patients with neuropsychiatric disorders including depression (Padala, Burke, & Bhatia, 2007), schizophrenia (Turner et al., 2004b), and Parkinson's disease (Happe, Pirker, Sauter, Klosch, & Zeitlhofer, 2001). Turner et al., (2004a) also found that modafinil enhanced cognitive functioning in ADHD patients, who after 2-3 hour post administration of modafinil, significantly improved on tests of short-term memory span, visual memory, spatial planning, and stop-signal motor inhibition. On several measures, modafinil increased sustained attention accuracy whilst slowing response latency.

However, most previous studies have significant shortcomings, as they only investigated the acute effect of modafinil on cognition and therefore are not able infer whether the same effects modafinil on cognitive function are consistently observed in subsequent testing sessions (Pubmed review 07/12/2009).

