Study Design: This is a double-blind, placebo-controlled, between subjects, parallel design study. 2 x 30 participants will receive either a single oral dose of a lactose placebo or 200mg of modafinil for four occasions (one dose per week to allow for drug washout). Participants will either be identified via the Behavioural and Clinical Neuroscience Institute participant panel or via an advertisement. Once potential participants are interested in taking part in the study, they will be sent an information sheet and contacted within 24 hours. Participants will be informed of the details of the study and will have the opportunity to ask questions or withdraw from it at any time.

Exclusion criteria: Prior to the first testing session, possible participants will be screened through telephone and any participant with any significant psychiatric history, visual or motor impairment or the concurrent use of any psychotropic medications or any medication contra-indicated with modafinil will be excluded. In addition, participants with a history of hypertension, cardiac disorders, epilepsy or drug or alcohol abuse will also be excluded. The two groups will be matched for age, verbal abilities by using the National Adult Reading Test, (Nelson, 1991) and education level. All participants will be advised not to consume alcohol or caffeine-containing drinks for 12 hours before the study.

Testing procedure: On a convenient date, participants will be asked to attend the WTCRF at Addenbrooke's Hospital on four occasions, separated by a maximum of one week. Once participants arrive at the WTCRF at about 8:30am, we will confirm their details and ask them to complete a personality and NART measures. After that, we will measure their blood pressure. Then we will give participants some capsules to swallow with water. These capsules will contain either a drug (modafinil), or a placebo (an inert lactose pill) –neither the participant nor the researcher testing the participant will know which pill participants are given on a particular day. A physician ([name]) will be available to provide medical assessment if participants experience any adverse events related to participation.

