- The Paired Associates Learning (PAL) task which tests the ability to learn and form visuo-spatial associations (Sahakian et al., 1988) (10 min)
- Pattern Recognition Memory (PRM) which is a two choice test of abstract visual pattern recognition memory (Mehta et al., 1999) (5 min).
- The Delayed Matching to Sample (DMTS) which is a 4 choice of simultaneous and delayed matching to sample abstract pattern task with distractors (Robbin et al., 1994) (10 min).
- The Rapid Visual Information Processing (RVIP) task measuring sustained attention (7 min)
- The 'one-touch' Tower of London spatial planning task (NTOL) which measures planning (Owen et al., 1995) (10 min) difficult version

Short self-report questionnaires, consisting of

- SF-8: SF-8 to measure participants' subjective wellbeing (5 min).
- Creative Personality Scale (CPS) for the Adjective Checklist by Gough's (1979) measuring whether participants are high or low in creativity(7 min).
- Visual Analogue Scale (VAS) (Bond & Lader, 1974) which assesses participants mood before, during and after the tablet administration (2 min).

Sample Size and Analysis: The Sample 30 per group was estimated to provide sufficient statistical power based on previous within-subject medication studies (Turner, 2003;). For a large effect size of modafinil study (d=0.52), the statistical power software (GPower) indicates a power of 0.95 to detect a large effect size with 0.05 error (i.e type I false positive error 5%) with 30 participants. A stronger interaction between modafinil and group (modafinil vs placebo x group) with a large effect size d=0.52, for false positives (a=0.05) with 30 participants in each group yields a power of 0.95. An interim analysis will be performed after the completion of the first sixteen participants in each group

Statistical analysis: All data will be analysed using Windows versions of SPSS (Version 15). To investigate the effect of experimental treatment on test performance, differences between group mean (or median) performance for group scores will be analysed using a one-way and repeated analysis of variance (ANOVA) or the equivalent non-parametric Kruskal-Wallis ANOVA. To clarify the nature of any such differences, planned orthogonal contrasts comparing the effect of modafinil, and the effect of placebo with the drug group, will be performed where appropriate. In instances where

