several readings are taken for the same score, repeated measures ANOVA will be used to test the effects of relevant independent within- and between-subjects variables. As our hypotheses are both one and two directional, all tests will employ two-tailed statistics threshold at p<0.05.

This is small scale study using modafinil as a pharmacological tool to neuromodulate cognitive performance and subjective wellbeing in healthy adults .It is therefore not a clinical trial under MHRA definitions.

Main Ethical Considerations:

Several areas have been considered here.

- 1. Confidentiality. We follow standard good research practices within our departments, to ensure confidentiality of electronic and hard copy data, in keeping with the Data Protection Act. Hard data are kept locked, and electronic data are anonymised and encrypted. We collaborate with other members of the University and require similar adherence to DPA and confidentiality by collaborators. We do not anticipate data sharing outside the UK. Data will be stored for maximum of 10 years within the department.
- 2. Safety. The safety of participants is paramount. This study involves a single standard dose (200mg) of modafinil, a medication with an excellent safety profile that is currently licensed for the treatment of daytime sleepiness. Modafinil has been used previously in multiple LREC-approved studies including male and female participants within the Department of Psychiatry (University of Cambridge) with no adverse reactions or problems reported. We have used modafinil with both patients (Backwell et al., 2008, CamREC reference number 04/076; Turner et al., 2004a, b) and Healthy adults (Winder-Rhodes et al., 2009-CamREC reference number 06/Q0106/47; Turner et al., 2003) and consistent with research evidence modafinil is safe (Deroche-Gamonet et al 2002; Billiard et al 1994) and current dose of modafinil has been well tolerated in studies run by members of our research team (e.g., Turner et al., 2009; Turner et al., 2004b). Furthermore, patients who are taking other forms of psychiatric or non-psychiatric medications contraindicated for use with modafinil will not be included in this study. The structured health interview as well as the information provided to participants will screen for pregnancy, breast-feeding, and volunteers who are attempting to become pregnant (see protocol and information sheet).

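### The sample size text calls its source within-subject, the Background describes separate groups, and neither reading of d=0.52 as a simple t-test effect gives the stated power of 0.95

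*Protocol*

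**What the plan says.** The Sample Size and Analysis paragraph of the protocol says that 30 per group was "estimated to provide sufficient statistical power based on previous within-subject medication studies". The one source cited is the 2003 healthy-volunteer study.

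The Background describes the participants of that study as "sixty young healthy male volunteers who either received a single oral dose of placebo, or 100mg, or 200mg of modafinil". The reference list holds only one 2003 modafinil study by that team, so both sections point to the same source.

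The effect size is introduced with the words "For a large effect size of modafinil study (d=0.52". No outcome, dose contrast, standard deviation or within-person correlation accompanies it. Power is stated twice. The software "indicates a power of 0.95 to detect a large effect size with 0.05 error" for 30 participants, and an interaction at the same d "with 30 participants in each group yields a power of 0.95".

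The trial itself is a "double-blind, placebo-controlled, between subjects, parallel design study" (Study Design), in which "2 x 30 participants will receive either a single oral dose of a lactose placebo or 200mg of modafinil". Under Statistical analysis, "all tests will employ two-tailed statistics threshold at p<0.05".

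**The concern.** A standardised effect from a within-subject study is usually divided by the SD of the paired differences. One from a parallel-group study is divided by the SD between people. The two are equal only when the within-person correlation is 0.5, so a within-subject value cannot be carried unchanged into a two-group design.

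The sample size text names neither the test nor the contrast behind 0.52, so the design label is the reader's only clue to its scale, and the Background contradicts that label. The effect size is the only quantitative support for 30 per group. Recomputing power at d=0.52 would correct the arithmetic but leave open whether 0.52 is the right input for this design.

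**Working it through.** **Inputs.** From Sample Size and Analysis: d = 0.52, alpha 0.05, 30 per group, stated power 0.95. From Statistical analysis: two-sided tests. From Study Design: two parallel groups. The within-person correlation r is not in the protocol; every value of it below is an assumption. Power is exact, from the noncentral t or F distribution.

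**1. The stated 0.95, taking 0.52 as a d**

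- Between-group d, one session: noncentrality = d × √(n/2) = 0.52 × √15 = 2.014; critical t on 58 df = 2.002; power = **0.51**.
- Within-subject d, paired test in 30 people: noncentrality = d × √n = 0.52 × √30 = 2.848; critical t on 29 df = 2.045; power = **0.79**.

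Neither gives 0.95. One-sided tests, which the protocol rules out, would give 0.64 and 0.87. With 30 per group, power of 0.95 needs a between-group d of about 0.95.

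**2. If 0.52 is a within-subject d**

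The equivalent between-group value is 0.52 × √(2(1 − r)). Power is for 30 per group at one session, two-sided.

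| Assumed r | Between-group d | Power |
|---|---|---|
| 0 | 0.74 | 0.80 |
| 0.3 | 0.62 | 0.65 |
| 0.5 | 0.52 | 0.51 |
| 0.7 | 0.40 | 0.34 |
| 0.8 | 0.33 | 0.24 |

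Below r = 0.5 the conversion raises power, above it lowers power, and at 0.5 it changes nothing.

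**3. If the source was parallel-group, as the Background says**

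The value is already on the between-person scale. No conversion is needed, and single-session power is 0.51.

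**4. If 0.52 is Cohen's f written as d**

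Noncentrality = f² × N = 0.2704 × 60 = 16.22.

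- Three groups, N = 60 (the layout the Background gives for the 2003 study): critical F = 3.16, power = 0.949.
- Two groups of 30: critical F = 4.01, power = 0.977.

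The first agrees closely with the stated 0.95. This is an inference from the numbers; the protocol does not say it.

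**5. Repeated measures**

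The protocol also plans repeated-measures ANOVA over four sessions. For the mean of four sessions at a between-group d of 0.52, the effective d is 0.52 / √((1 + 3r)/4), where r is now the correlation between sessions. Power with 30 per group is 0.98, 0.82, 0.71 and 0.54 at assumed r of 0, 0.3, 0.5 and 0.9. For a group-by-session interaction with f = d/2 = 0.26 and N = 60, power is 0.93 at r = 0 and 0.99 at r = 0.3. Values near 0.95 can thus be reached, but only by adding a correlation, and for the interaction an effect-size convention, that the protocol does not state.

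**The case against.** The strongest reply is that this is one wrong adjective. If the Background is right, the source was parallel-group, its d is already on the scale this trial needs, and no scale error exists. That stands as a possibility, so the contradiction does not prove that 0.52 is on the wrong scale. It shows only that the scale cannot be established from the protocol.

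Second, 0.52 is not firmly tied to the 2003 study. The text refers to studies in the plural, the citation ends in a stray semicolon, and d is attributed to an unnamed modafinil study. A dropped second reference is plausible. This stands too, and the fix allows for it.

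Third, the protocol plans repeated-measures analyses, for which single-session power is not the whole picture. That is fair, but the sample size text states no correlation or averaging, so it does not explain 0.95.

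Two stronger readings are tempting, and the document supports neither.

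- A reader might infer that 0.52 is too small to be one of the improvements the Background calls significant. With an assumed 20 per arm and an unadjusted two-sided t test, significance needs d of at least 2.024 × √(2/20) = 0.64, or 2.002 × √(1/40 + 1/20) = 0.55 with both doses pooled. But the Background gives no allocation, test or sidedness. Pooled and one-sided, the threshold is 0.46. A planning value may also be set below an observed effect on purpose.
- A reader might infer that a scale error would usually flatter the power. That needs r above 0.5, and the protocol gives no r.

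**Conclusion.** The concern holds in a limited form. The design label of the only cited source is contradicted within the protocol, and with no outcome or contrast named the metric of 0.52 cannot be determined.

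Separately from the label, the stated 0.95 is wrong for either simple reading of d: 0.51 for two groups of 30 at one session, and 0.79 for a paired test in 30 people. These two figures use only inputs printed in the protocol. The range from 0.80 down to 0.24 applies only if 0.52 is a within-subject d, and rests on assumed correlations from 0 to 0.8. A scale error could move power in either direction, or not exist at all if the source was parallel-group. The Cohen's f explanation fits the stated figure well but remains conjecture.

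The sponsor should correct this, because the figure is the protocol's only numerical justification for the group size. It does not by itself show that the effect assumed is too large or too small.

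**What to change.** 1. Make the Background and the Sample Size and Analysis paragraph agree on the design of the 2003 study, or cite the study that actually supplied 0.52.
2. Say which metric 0.52 is (within-subject d, between-group d or Cohen's f) and which test and contrast it came from. Express it relative to the between-person SD, converting if needed.
3. Replace 0.95 with the power this gives for the two-group design. If 0.52 is a between-group d, that is 0.51 for one session with 30 per group. If it is a within-subject d and r cannot be recovered, quote the range 0.80, 0.65, 0.51, 0.34, 0.24 for assumed r of 0, 0.3, 0.5, 0.7, 0.8.
4. If the power is meant for a repeated-measures effect, state the effect tested and the assumed correlation between sessions.

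The cost is wording and a recalculation. No more participants are needed for this correction; the downside is that the stated power is likely to be less favourable.

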Research Protocol

THE EFFECT OF MODAFINIL ON CONGITION AND SUBJECTIVE WELLBEING IN HEALTHY ADULTS

Chief and Principal Investigator

[name], Professor of Clinical Neuropsychiatry, Cambridge School of Clinical Medicine & Behavioural and Clinical Neuroscience Institute University of Cambridge, Department of Psychiatry, Addenbrooke's Hospital [name] [contact] Email: [contact]

Research Team:

[name], Department of Experimental Psychology & BCNI, University of Cambridge (Head of Experimental Psychology, University of Cambridge)

[name], Department of Clinical Neurosciences & BCNI, Honorary Consultant neurologist at the Cambridge University Neurology Unit & MRC Cognition and Brain Sciences Unit

[name], Department of Psychiatry & BCNI, University of Cambridge,

Aims of the Project

This project aims to investigate the effect of modafinil on cognitive performance, divergent thinking and subjective well-being in healthy participants. The main task for this project is to address whether the same effects of acutely administered modafinil on cognitive function are observed across four testing sessions or whether its effects exhibit tolerance. Participants' divergent thinking, cognitive performance and subjective well-being will be investigated in a between-subjects parallel design study.

Two groups each of 32 healthy participants will attend four separate sessions at the Wellcome Trust Clinical Research Facility (WTCRF), during which they will be tested on objective measures of divergent thinking tasks, a computerised neuropsychological battery, and on well-validated questionnaires quantifying subjective well-being. Participants will be randomly allocated to one group and will consistently receive either a dose of modafinil (200mg) (Modafinil group) or a placebo (Control group) prior to testing on all four sessions.

All subjects will undertake CANTAB tests and different versions of the divergent thinking tasks. Based on the evidence that modafinil enhances executive planning and working memory in healthy adults (Turner et al 2003), we predict that healthy individuals in the Modafinil group will perform better in the divergent thinking tasks and in the cognitive performance tasks. Furthermore, we expect a specific subjective well-being effect to be associated with recurrent modafinil use in healthy young adults.

Background

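### The stated power of 0.95 is wrong for the parallel-group comparison at d=0.52 (0.51 at one session with 30 per group); the interaction power cannot be verified; and group size is both 30 and 32

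*Protocol*

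**What the plan says.** The sample size paragraph (Protocol, Sample Size and Analysis) makes two power statements.

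- The first reads "For a large effect size of modafinil study (d=0.52), the statistical power software (GPower) indicates a power of 0.95" and continues "to detect a large effect size with 0.05 error (i.e type I false positive error 5%) with 30 participants". The sentence before it gives the size as 30 per group, "estimated to provide sufficient statistical power based on previous within-subject medication studies", and cites one study from 2003.
- The second concerns an interaction, again with d=0.52: "for false positives (a=0.05) with 30 participants in each group yields a power of 0.95". In brackets it defines the interaction as the modafinil-versus-placebo contrast crossed with group.

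The design is between-subjects and parallel (Aims of the Project; Study Design), with four weekly sessions. The Statistical analysis paragraph plans one-way and repeated-measures ANOVA and says "all tests will employ two-tailed statistics threshold at p<0.05".

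The Background describes the cited 2003 study as "sixty young healthy male volunteers who either received a single oral dose of placebo, or 100mg, or 200mg of modafinil".

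On group size, the Aims say "Two groups each of 32 healthy participants will attend four separate sessions", while Study Design says "2 x 30 participants will receive either a single oral dose".

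**The concern.** The power paragraph is the only justification for the sample size. A standardised difference of 0.52 between two independent groups of 30 sits almost exactly at the two-sided 5% significance boundary, so its power should be near one half, not 0.95. The label large also fits badly: by the usual convention a d near 0.5 is medium.

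The stated basis does not match the Background either. Volunteers who each received one of three single doses form a between-subjects layout, not a within-subject one.

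Two things are at stake. Readers are told that the trial can detect d=0.52 with near certainty when, for the group comparison, it cannot. And the recruitment target is not defined, because two group sizes stand side by side.

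**Working it through.** **Inputs from the protocol:** d=0.52, alpha 0.05, 30 per group (Sample Size and Analysis); 32 per group (Aims); two-tailed tests (Statistical analysis); two parallel groups and four sessions (Aims; Study Design). **Not given:** between-session correlation, number of measurements used in the power calculation, and GPower test family. Correlations below are assumptions.

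**1. Trying to reproduce 0.95 at one session.** The two-sample t-test has noncentrality δ = d·√(n/2) on 2n−2 degrees of freedom.

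- n=30: δ = 0.52 × √15 = 2.014, df 58. The normal approximation gives Φ(2.014 − 1.960) = Φ(0.054) = 0.522; exact noncentral t gives 0.508.
- n=32: δ = 0.52 × √16 = 2.08, df 62. Normal approximation 0.548; exact 0.535.

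Other readings of the same inputs (exact t):

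| Reading | Power |
|---|---|
| Two-sample, 30 per group, one-sided | 0.635 |
| Two-sample, 30 in total (15 per group), two-sided | 0.280 |
| Paired, n=30, two-sided | 0.786 |
| Paired, n=30, one-sided | 0.872 |
| 0.52 read as Cohen's f (d = 2 × 0.52 = 1.04), 30 per group, two-sided | 0.977 |

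None gives 0.95.

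**2. What 0.95 would need at one session.** At d=0.52 it takes 98 per group (exact t; 97 by the normal approximation). With 30 per group it takes d=0.947, and with 32 per group d=0.916.

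**3. Mean of four sessions.** With f = d/2 = 0.26, total N=60, m=4 sessions and correlation ρ, the between-group F test has λ = f²·N·m/(1+(m−1)ρ) = 0.0676 × 60 × 4/(1+3ρ) = 16.224/(1+3ρ), on 1 and 58 df.

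| ρ (assumed) | λ | Power, 30 per group | Power, 32 per group |
|---|---|---|---|
| 0.3 | 8.54 | 0.82 | 0.84 |
| 0.5 | 6.49 | 0.71 | 0.74 |
| 0.7 | 5.23 | 0.61 | 0.64 |

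With 30 per group, power is 0.954 at ρ=0.06 and 0.945 at ρ=0.08. So 0.95 needs almost no correlation between repeated scores from the same person.

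**4. The interaction.** For group by session, λ = f²·N·m/(1−ρ) on m−1 and (N−2)(m−1) df. Taking f=0.26 here is itself an assumption.

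- N=60, m=4: λ = 16.224/(1−ρ). Power is 0.932 at ρ=0, 0.951 at 0.08, 0.987 at 0.3 and 0.999 at 0.5.
- N=60, m=2: λ = 8.112/(1−ρ). Power is 0.951 at ρ=0.4.
- N=30 in total, m=4: λ = 8.112/(1−ρ). Power is 0.95 at ρ=0.55.

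At least three quite different settings give 0.95, and the protocol identifies none of them. As worded, the term crosses treatment with group, but in this design group is treatment, so the tested effect is not defined.

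**The case against.** The strongest reply is that 51% belongs to the least favourable planned analysis. The protocol names tolerance across four sessions as its main question and plans repeated-measures ANOVA. For a group-by-session interaction, 0.95 or more is attainable under ordinary correlations. This part stands. A reader might infer that the whole design has only 51% power, or that both 0.95 figures are wrong. The documents support neither: 51% is for one session, averaging sessions raises it, and the interaction figure is only unverifiable. The single-session comparison still matters, because the predictions expect improvement in divergent thinking at least in the first session and contrast that session with the other three.

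Three further inferences are tempting and should not be drawn.

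- **That d and f were confused.** The label large would suit f, but f=0.52 gives 0.977 with 30 per group, not 0.95, and no GPower inputs are shown. The cause is unknown.
- **That 0.52 is a paired effect which shrinks in a parallel design.** The protocol does not say so. If it were, d_between = 0.52·√(2(1−ρ)) would be 0.40, 0.52 or 0.62 at assumed ρ of 0.7, 0.5 or 0.3, with power 0.33, 0.51 or 0.65. The conversion can go either way.
- **That an interim after sixteen per group proves 32 was intended.** The protocol never says that the interim falls at the halfway point.

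It is also fair that the basis refers to studies in the plural and that its citation looks unfinished, so other sources may have been meant. The mismatch is shown only for the one study cited. The 30/32 discrepancy is small in effect, moving single-session power from 0.508 to 0.535, and it does not rescue the stated figure.

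**Conclusion.** The concern holds in this limited form. For the two-sided parallel-group comparison at d=0.52 and alpha 0.05, the stated 0.95 is wrong. Single-session power is 0.51 with 30 per group, 44 percentage points lower. The mean of four sessions gives about 0.61 to 0.82 for assumed correlations of 0.7 to 0.3, which is 13 to 34 points lower. The single-session result rests only on the protocol's own inputs; the four-session result also rests on the assumed correlations and on equal correlation between sessions.

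The second 0.95 is neither confirmed nor refuted: its effect, number of measurements, correlation and test family are not stated. The within-subject label contradicts the Background for the one study cited, and the group size contradicts itself.

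A reader might go on to infer that a null result would be taken as evidence of no effect. The protocol states no such interpretation. What can be said is that, if d=0.52 is true, one single-session comparison misses it about half the time, and a comparison of four-session means misses it about 18% to 39% of the time under the assumed correlations.

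This should be corrected, because figures given in the protocol itself disagree. It is not a detail that could be left to an analysis plan.

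**What to change.** Amend the wording as follows.

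1. Choose 30 or 32 per group and use it in the Aims, Study Design and Sample Size sections.
2. Replace the first power statement with what the design delivers. For example, with 30 per group: power is 51% for d=0.52 at a single session (two-sample t-test, two-sided 0.05) and reaches 95% only for d of about 0.95 or more. If 32 is chosen, the figures are 54% and about 0.92. If power for the mean of four sessions is quoted, state the assumed correlation with it.
3. Say whether 0.52 is d or f. If it is d, drop the label large. If it is f, state the equivalent d=1.04 and the corresponding power of 0.98 with 30 per group.
4. Give the group-by-session interaction power separately, since change across sessions is the main aim. State its effect-size definition, number of sessions, assumed correlation and test family, and replace the term that crosses treatment with group.
5. Correct the within-subject basis, or cite the within-subject studies that were meant and explain how their effect size was carried over to a parallel design.

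The cost is protocol text and a less favourable stated power. No extra participants, visits or design changes are needed.
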